## **Vernakalant IV Sterile Concentrate Prospective Safety Registry Study**

Sponsor Protocol Identifier: 6621-049-00

3 August 2016

---

\* "Clinically meaningful" events included serious adverse events (SAEs) and events leading to discontinuation of therapy.

In these studies, hypotension typically occurred early, either during the infusion or early after the end of the infusion, and could usually be corrected by standard supportive measures. Ventricular arrhythmias typically presented as asymptomatic, monomorphic, non-sustained (average 3-4 beats) ventricular tachycardias. Bradycardia was observed predominantly at the time of conversion to sinus rhythm. In general, bradycardia responded well to discontinuation of vernakalant and/or administration of atropine.

Due to the higher incidence of hypotension and ventricular arrhythmia in patients with CHF, vernakalant should be used cautiously in haemodynamically stable patients with CHF functional classes NYHA I to II. There is limited experience with the use of vernakalant in patients with previously documented LVEF  $\leq$  35% and its use in these patients is not recommended. The use of vernakalant IV in CHF patients corresponding to NYHA III or NYHA IV is contraindicated.

These clinically significant adverse reactions are being monitored as identified and potential risks in the vernakalant Risk Management Plan (RMP). In addition, although there were no examples of vernakalant IV overdosing in the clinical trials, in consideration of the logistical complexity of weight-based dosing regimens such as that used for vernakalant, potential risk of overdose is also being monitored through the RMP.

Vernakalant IV was approved 1 September 2010 by the European Commission for rapid cardioversion of recent onset AF (<=3 days duration for post-cardiac surgery and <=7 days duration for non-surgical patients).

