- Severe bradycardia in the absence of a pacemaker
- Sinus node dysfunction in the absence of a pacemaker
- Heart block (second or third degree) in the absence of a pacemaker
- Patients with heart failure NYHA functional class III or NYHA functional class IV
- Use of class I or class III intravenous anti-arrhythmics within four hours prior to or after the start of vernakalant administration other presenting conditions and medical history at baseline will be summarised.

The following presenting conditions and medical history information will be reported in term of number and percentage (**Table 5**):

Presenting Conditions:

- Systolic blood pressure (mm Hg) as recorded most immediately prior to initial vernakalant infusion
- Diastolic blood pressure (mm Hg) as recorded most immediately prior to initial vernakalant infusion
- Heart rate (beats per minute) as recorded most immediately prior to initial vernakalant infusion)
- New York Heart Association (NYHA) functional class at hospital presentation (0, I, II, III, IV)

- History of heart failure (yes, no, unknown) and among these patients who had NYHA heart failure class III or IV at hospital presentation
- Previously documented left ventricular ejection fraction (LVEF, $\leq 30\%$, $> 30 - \leq 50\%$, $> 50\%$, Not Available). LVEF information will be reported as recorded in the electronic case report form (eCRF) from either (1) the baseline echocardiogram (performed during the index hospitalization, but prior to vernakalant administration), if available, or (2) the baseline medical history CRF, which records previously documented LVEF for patients with a reported history of heart failure. If data are available in both forms, the data with the most recent associated date will be included. Otherwise patients will be classified as LVEF $> 35\%$ or “not available”. The “not available” classification includes patients with no LVEF information on either the medical history or echocardiogram data collection forms. Additional details regarding LVEF (%), such as range of LVEF, may be reported, if available.
- Clinically meaningful valvular stenosis, as per physician assessment (yes, no, unknown), and among these patients who have a history of valve replacement and had heart valve surgery during index hospitalisation
- Cardiomyopathy (yes, no, unknown, and whether hypertrophic obstructive cardiomyopathy, restrictive cardiomyopathy or other)
- Constrictive pericarditis (yes, no, unknown)

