| History of heart failure² | | | |
| n | XXX | XXX | XXX |
| Yes | xx (xx.x%) | xx (xx.x%) | xx (xx.x%) |
| NYHA heart failure class III or IV at Presentation ³ | xx (xx.x%) | xx (xx.x%) | xx (xx.x%) |
| No | xx (xx.x%) | xx (xx.x%) | xx (xx.x%) |
| Unknown | xx (xx.x%) | xx (xx.x%) | xx (xx.x%) |

| Characteristic | Analysis Set (N=xxx) | Prospective Patients (N=xxx) | Retrospective Patients (N=xxx) |
|---|-------------------------|------------------------------------|--------------------------------------|
| Missing | xx | xx | xx |
| Previously documented left ventricular ejection fraction⁴ | | | |
| n | xxx | xxx | xxx |
| ≤30 % | xx (xx.x%) | xx (xx.x%) | xx (xx.x%) |
| >30 -≤ 50% | xx (xx.x%) | xx (xx.x%) | xx (xx.x%) |
| >50% | xx (xx.x%) | xx (xx.x%) | xx (xx.x%) |
| Not available | xx (xx.x%) | xx (xx.x%) | xx (xx.x%) |
| Missing | xx | xx | xx |
| Clinically meaningful valvular stenosis | | | |
| n | xxx | xxx | xxx |
| Yes | xx (xx.x%) | xx (xx.x%) | xx (xx.x%) |
| History of valve replacement | xx (xx.x%) | xx (xx.x%) | xx (xx.x%) |
| Heart valve surgery during index hospitalisation | xx (xx.x%) | xx (xx.x%) | xx (xx.x%) |
| History of valve replacement and heart valve surgery during index hospitalisation | xx (xx.x%) | xx (xx.x%) | xx (xx.x%) |
| No | xx (xx.x%) | xx (xx.x%) | xx (xx.x%) |
| Unknown | xx (xx.x%) | xx (xx.x%) | xx (xx.x%) |
| Missing | xx | xx | xx |
| Cardiomyopathy | | | |
| n | xxx | xxx | xxx |
| Yes | xx (xx.x%) | xx (xx.x%) | xx (xx.x%) |
| No | xx (xx.x%) | xx (xx.x%) | xx (xx.x%) |
| Unknown | xx (xx.x%) | xx (xx.x%) | xx (xx.x%) |
| Missing | xx | xx | xx |
| Specify type, if yes | | | |
| n | xx | xx | xx |
| Hypertrophic obstructive | xx (xx.x%) | xx (xx.x%) | xx (xx.x%) |
| Restrictive | xx (xx.x%) | xx (xx.x%) | xx (xx.x%) |
| Other | xx (xx.x%) | xx (xx.x%) | xx (xx.x%) |
| Missing | xx | xx | xx |
| Constrictive pericarditis | | | |
| n | xxx | xxx | xxx |
| Yes | xx (xx.x%) | xx (xx.x%) | xx (xx.x%) |
| No | xx (xx.x%) | xx (xx.x%) | xx (xx.x%) |
| Unknown | xx (xx.x%) | xx (xx.x%) | xx (xx.x%) |
| Missing | xx | xx | xx |
| Advanced hepatic impairment⁵ | | | |
| n | xxx | xxx | xxx |
| Yes | xx (xx.x%) | xx (xx.x%) | xx (xx.x%) |
| No | xx (xx.x%) | xx (xx.x%) | xx (xx.x%) |
| Unknown | xx (xx.x%) | xx (xx.x%) | xx (xx.x%) |
| Missing | xx | xx | xx |

| Characteristic | Analysis Set (N=xxx) | Prospective Patients (N=xxx) | Retrospective Patients (N=xxx) |

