³ Number of patients with NYHA heart failure class III or IV (as assigned by physicians at presentation) among those with heart failure recorded in the baseline medical history CRF.

⁴ Left ventricular ejection fraction (LVEF) reported as recorded in the baseline echocardiogram CRF, if available or the baseline medical history CRF for patients with reported history of heart failure, if available. If data are available in both forms, the data with the most recent associated date was included. The "not available" classification includes patients with no LVEF information on either the medical history or echocardiogram data collection forms.

⁵ Advanced hepatic impairment is physician-reported based on question, "Does the patient currently have any of the following presenting conditions: advanced hepatic impairment (yes, no, unknown)."

⁶ Elevated liver enzymes (inclusive of possible abnormal liver function or liver injury), defined as an increase above upper limit of normal (ULN) for alanine aminotransferase, aspartate aminotransferase, or total or conjugated bilirubin based on recommended algorithms to classify abnormal liver function and liver injury in the literature. Patients must have at least one laboratory value available for alanine aminotransferase, aspartate aminotransferase, total bilirubin or conjugated bilirubin to be included.

⁷ Estimated Glomerular Filtration Rate (eGFR) will be calculated using Modification of Diet in Renal Disease (MDRD) for patients with available race information.

Table 6 Atrial Fibrillation (AF) Disease History and Current Episode

| Characteristic | Analysis Set (N=xx) | Prospective Patients (N=xx) | Retrospective Patients (N=xx) |
|--|------------------------|-----------------------------------|-------------------------------------|
| Duration of current AF (hours)¹ | | | |
| n | xx | xx | xx |
| Mean (SD) | xx (xx) | xx (xx) | xx (xx) |
| Median | xx | xx | xx |
| Q1, Q3 | xx,xx | xx,xx | xx,xx |
| Min, Max | xx,xx | xx,xx | xx,xx |
| Missing | xx | xx | xx |
| Duration of current AF (hours, categorical)¹ | | | |
| n | xx | xx | xx |
| <3 hours | xx (xx.x%) | xx (xx.x%) | xx (xx.x%) |
| 3-24 hours | xx (xx.x%) | xx (xx.x%) | xx (xx.x%) |
| 24-48 hours | xx (xx.x%) | xx (xx.x%) | xx (xx.x%) |
| 48-168 hours (7 days) | xx (xx.x%) | xx (xx.x%) | xx (xx.x%) |
| ≥168 hours (7 days) | xx (xx.x%) | xx (xx.x%) | xx (xx.x%) |
| Missing | xx | xx | xx |
| Time since first AF diagnosis (days)² | | | |
| n | xx | xx | xx |

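### The planned LVEF categories can only bound the number treated at LVEF ≤35%, and the SAP's >35% default matches no category in its list or in Table 5

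*SAP*

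**What the plan says.** **Protocol, Section 3 (Background).** The text on heart failure states: "There is limited experience with the use of vernakalant in patients with previously documented LVEF" at or below 35%. It goes on, "35% and its use in these patients is not recommended". NYHA class III or IV is treated separately, as a contraindication.

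**SAP, Section 5.8, presenting conditions.** The bullet that opens "Previously documented left ventricular ejection fraction (LVEF" lists four categories: ≤30%, >30 to ≤50%, >50% and not available. The value comes from the baseline echocardiogram or, for patients with a reported history of heart failure, from the medical history form. If both forms hold data, the more recent one is used. The bullet then says "Otherwise patients will be classified as LVEF" above 35%, or not available. It defines the latter: the "classification includes patients with no LVEF information on either the medical history or echocardiogram data collection forms". It closes by saying that further detail, "such as range of LVEF, may be reported, if available".

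**SAP, Appendix 1, Table 5.** The block headed "Previously documented left ventricular ejection fraction" has rows for ≤30%, >30 to ≤50%, >50%, not available and missing. Footnote 4 repeats the source rule ("If data are available in both forms, the data with the most recent associated date was included") and goes straight on to the definition of not available. It has no >35% default.

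**The concern.** There are two separate problems.

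1. The protocol attaches a caution to one LVEF threshold, and the only planned summary of LVEF is cut at two others. Primary Objective 3 asks whether patients were selected in line with the label and the risk minimisation activities. SAP Section 5.6 frames this as compliance with key aspects of the SmPC and sends patient selection partly to Section 5.8. A reader of the final report would reasonably look there for the number treated at LVEF ≤35%. Table 5 as laid out does not give it.

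2. The SAP bullet tells the programmer to use a category that neither its own list nor the table contains. If the instruction were followed for patients with no LVEF on file, unknown values would be reported as being on the favourable side of the threshold. SAP Section 4.4 rules out imputation. Values may often be absent: Protocol Section 7.1.1 collects baseline LVEF only if it was measured in usual care, and the medical history form supplies it only for patients with known heart failure.

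**Working it through.** The plan gives no figure to reproduce. The check is whether the planned rows can yield the protocol's group, and whether the default rule can be carried out.

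**Inputs**
- Threshold: LVEF ≤35% (Protocol Section 3).
- Rows: ≤30%, >30 to ≤50%, >50%, not available (SAP Section 5.8; Table 5, which adds a missing row).
- Default: >35% or not available (SAP Section 5.8 only).
- Not available: no LVEF on either form (SAP Section 5.8; Table 5 footnote 4).

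**Step 1: can the rows be combined to give the threshold?** Whole-number LVEF values from 5 to 80 were assigned to the three numeric rows, and every combination of rows was compared with the two target groups.

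| Group wanted | Rows it falls in | Does any combination of rows equal it? |
|---|---|---|
| LVEF ≤35% | ≤30; >30 to ≤50 | No |
| LVEF >35% | >30 to ≤50; >50 | No |

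For example, values of 33% and 45% lie on opposite sides of the threshold but share the middle row.

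**Step 2: what the table does tell us.** Let a be the count at ≤30% and b the count at >30 to ≤50%. Among patients with a value,

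a ≤ n(LVEF ≤35%) ≤ a + b.

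The width of this interval is (a + b) − a = b, the whole middle row. The same holds in the prospective and retrospective columns, and in the country versions of Table 5 that SAP Section 4.3 requires.

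**Step 3: can the default be applied?** The sentence does not say who falls under it. There are three possible readings:

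- *Patients with data on one form only.* They have a recorded value and belong in a numeric row. Labelling them >35% could override that value.
- *Patients with data on neither form.* The next sentence places them in not available. Labelling them >35% would contradict it, and would assign a value despite SAP Section 4.4.
- *Patients whose LVEF was noted but not as an exact percentage.* The label >35% might be true, but it spans the >30 to ≤50 and >50 rows, so the patient still has no row.

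No reading gives a >35% patient a defined place in Table 5. Footnote 4, which lacks the sentence, can be programmed as it stands.

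**Step 4: is LVEF reported elsewhere?** It is absent from Table 11, from the exclusions for the SmPC subgroup (SAP Section 4.3) and from the missing-data table (Table 18). Table 5 is the only planned summary.

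**Step 5: after the change.** With rows ≤35%, >35 to ≤50% and >50%, n(LVEF ≤35%) is read directly and the interval closes. If ≤30% is kept as a sub-row, the current middle row is recovered as n(≤35) − n(≤30) + n(>35 to ≤50), so no present output is lost.

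**The case against.** The strongest reply is that LVEF ≤35% is not a selection criterion in this plan. SAP Section 5.6 glosses appropriate selection as adherence to indications and contraindications, which Tables 10 and 11 cover. The protocol calls the LVEF group not recommended, as distinct from contraindicated. LVEF is not among the contraindications listed as monitored in Protocol Section 3, the exclusions in the German annex, or the conditions named under Secondary Objective 2. The 35% sentence sits in the Background and is not itself attributed to the SmPC, which is not among the documents. Much of this stands: leaving LVEF out of Table 11 is not an error, and what can be shown is a mismatch with the protocol's own threshold. It does not remove the point, because Section 5.6 also speaks of key aspects of the SmPC and sends selection to Section 5.8, where LVEF is reported.

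A second reply is that the plan leaves room for the count: further LVEF detail may be reported, and SAP Section 5 allows ad hoc analyses on request. So it would be too strong to infer that the number at ≤35% could never be obtained. Both routes are discretionary and neither names 35%. The planned shell simply does not guarantee the count.

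A third reply is that the default probably does little, since the following sentence and footnote 4 already place patients with no value. That is likely, but the contradiction remains in the text given to the programmer.

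**Conclusion.** The point holds as a reporting defect of modest size. The planned table bounds the number treated at LVEF ≤35%, with an uncertainty equal to the whole >30 to ≤50% row, and the >35% default has no row and conflicts with other SAP text if applied to patients without a value. The reach is limited to the descriptive assessment of patient selection under Primary Objective 3 and Secondary Objective 2. The incidence of health outcomes of interest, Tables 10 and 11 and the effectiveness results do not depend on it.

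Three stronger readings are tempting and are not supported:

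- *Patients above 30% and up to 35% are misclassified, and not-recommended use is undercounted.* They sit in a row that straddles the threshold. No row claims to count not-recommended use, so no planned count is understated.
- *A definite number of patients is hidden.* The documents give no LVEF distribution. The 2,000 target is the wrong base, because many patients may have no recorded LVEF.
- *The default is a remnant of a superseded 35% cut.* That is plausible, but no document states it.

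The conclusion rests on the wording of the three places set side by side. The one open fact is how the eCRF stores LVEF. The SAP's mention of LVEF (%) suggests a numeric field but does not settle it.

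**What to change.** 1. In SAP Section 5.8 and Table 5, including the country versions, report LVEF as ≤35%, >35 to ≤50%, >50% and not available. Keep ≤30% as an optional sub-row.
2. Check the eCRF field format. Then either delete the >35% default or define exactly whom it covers and reconcile it with footnote 4. In either case, patients with no LVEF on either form go to not available.

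If LVEF is stored as a percentage, the cost is one sentence of SAP text and one changed table row, with no new data. If some values were recorded only as above or below a threshold, those patients also need a stated row. The change affects reporting only. It takes the threshold from the protocol and proposes no clinical rule.

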5.10 Secondary Objective #4: Rate of Conversion to Sinus Rhythm

For patients in the analysis population set and the effectiveness analysis population set, the rate of successful conversion to sinus rhythm for at least one minute within 90 minutes from the start of first vernakalant IV administration (Secondary Objective 4) will be expressed as the proportion of patients with successful conversion, together with the associated 95% confidence interval. (**Table 15a**). The rate of successful conversion to sinus rhythm without time restriction will also be expressed as the proportion of patients with successful conversion, together with the associated 95% confidence interval. The time (in minutes) from start of vernakalant infusion to conversion to sinus rhythm among those patients who converted will be summarised using appropriate measures of dispersion and central tendency (means, medians, ranges, Q1-Q3 ranges, and standard deviations) (**Figure 3**). As defined in Section 4.3, a pre-specified secondary analysis of the effectiveness of vernakalant will be restricted to a subgroup of patients who receive vernakalant IV in accordance with the SmPC (i.e., adult indication, therapeutic indication for AF, duration of AD \leq 7 days for non-surgery patients and \leq 3 days for post-cardiac surgery patients, and no contraindications) (**Table 15b**). Rates of successful conversion will also be

tabulated for all patients by non-surgery and post-cardiac surgery indications, respectively (**Table 15c, 15d**).

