## **7 DATA COLLECTION**

### **7.1 Collection of Required Data Elements**

Scheduled assessments for the study are presented in the Registry Assessment Flow Chart provided in this section. All data elements will be collected from information routinely recorded in the medical record, or will be prospectively recorded by the investigator for the purposes of the study.

Data will be collected via an electronic case report form (eCRF). Data describing vernakalant IV administration and dosing at baseline, and observations during study follow-up (from start of first infusion through the 24-hour period following last infusion of vernakalant IV or discharge/end of medical encounter, whichever is earlier) will be collected; site personnel will enter (or transfer if collected on a paper case report form) the collected data in the appropriate eCRFs. Information on concomitant medications and administration of other therapies to restore/maintain sinus rhythm during the index hospitalization for stays exceeding 24 hours following last infusion of vernakalant IV will be collected, up to a maximum of 7 days following last infusion of vernakalant IV. For prospectively recorded data elements, expected to include NYHA class [Ref. 5.4: 443] and elements of medical history at presentation which may not be available in the medical record, the investigator will record the data in the eCRF and add any

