3.3 Effectiveness Outcome: Conversion to Sinus Rhythm

Effectiveness of vernakalant IV will be assessed as a secondary endpoint, defined as the proportion of patients who are converted to sinus rhythm for at least one minute within 90 minutes of start of first vernakalant IV administration. Additionally, the proportion who are converted to sinus rhythm regardless of timing will be reported. (Refer to Section 4.3 for description of further effectiveness subgroup analyses per Summary of Product Characteristics (SmPC)).

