4.2 Analysis Populations

All screened patients will be included in summary of patient disposition with additional summary of their demographic characteristics. All enrolled patients who meet the eligibility criteria, sign the informed consent form, and are administered vernakalant IV will be included in the analysis population set, regardless of their disposition status. If a patient's consent is withdrawn prior to completing follow-up period, all data already collected as part of the study will be retained for analysis unless country-specific ethics committee (EC) requirements prohibit this or the patient requests otherwise. In addition, patients who discontinue from the study prior to receiving vernakalant administration will not be included in the overall analysis population. All the summaries will be presented on the overall analysis population set unless otherwise stated.

Patients may be enrolled in the study more than once in association with multiple administrations of vernakalant IV. Patients with multiple enrolments are included in the analysis population, and the number of previous study enrolments is provided in the study analysis. All study analyses presented in the study tables, listings, and figures of this report treat each patient's subsequent administrations of vernakalant IV as occurring independently.

Effectiveness analysis population is defined as all patients from overall analysis population defined above EXCEPT those who receive ECV or IV Class I/III AA for cardioversion within 90 minutes of start of the first vernakalant IV administration. But for analysis of the effectiveness of

vernkalant IV, e.g., rate of conversion, both analysis population and effectiveness population may be used.

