¹ Includes patients who receive more than 1 infusion within a single treatment episode.

² Rate of conversion (%) is calculated as: (number of patients who have conversion to sinus rhythm for at least one minute with 90 minutes after first vernakalant infusion within effectiveness analysis population) / (total number of patients within effectiveness analysis population) x 100.

³ Rate of conversion (%) is calculated as: (number of patients who, within 90 minutes after first vernakalant infusion, have conversion to sinus rhythm for at least one minute but have no ECV or IV Class I/III AA within overall analysis population) / (total number of patients within overall analysis population).

⁴ Rate of conversion (%) is calculated as: (number of patients who, within 90 minutes after first vernakalant infusion, have conversion to sinus rhythm for at least one minute but have no ECV, oral propafenone/flecainide or IV Class I/III AA within overall analysis population) / (total number of patients within overall analysis population).

Template of Table 15a will be applied to the following three tables.

Table 15b Proportion of Patients Converted to Sinus Rhythm and Time to Conversion Following Vernakalant Infusion (SmPC Subgroup Analysis)

Table 15c Proportion of Patients Converted to Sinus Rhythm and Time to Conversion Following Vernakalant Infusion (Non-Surgery Patients)

Table 15d Proportion of Patients Converted to Sinus Rhythm and Time to Conversion Following Vernakalant Infusion (Post-Cardiac Surgery Patients)

Table 16.1a.1 Serious Adverse Events (System Organ Class and Preferred Term) by Outcome (Analysis Set) – Investigator Assessment

| | Analysis Set (N=xxx) Outcome | | | | | | | |
|---|---|----------|---|----------|---|----------|---|----------|
| | Recovered | | Recovered with Sequelae | | Not Recovered | | Overall | |
| System Organ Class/ High Level Term/ Preferred Term | Patients n (Cumulative Incidence ¹) | Events n | Patients n (Cumulative Incidence ¹) | Events n | Patients n (Cumulative Incidence ¹) | Events n | Patients n (Cumulative Incidence ¹) | Events n |
| Any SAE | xx (x.x%) | xx |
| SOC 1 | xx (x.x%) | xx |
| HLT 1 | xx (x.x%) | xx |
| PT 1 | xx (x.x%) | xx |
| PT 2 | xx (x.x%) | xx |
| SOC 2 | xx (x.x%) | xx |
| HLT 2 | xx (x.x%) | xx |
| PT 1 | xx (x.x%) | xx |
| PT 2 | xx (x.x%) | xx |

Note: SAE events include reported HOIs that are mapped to specific MedDRA terms.

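### The SAP's conversion rate without time restriction has no rule for other cardioversion after 90 minutes, so later rescue successes can be counted as vernakalant conversions

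*SAP*

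**What the plan says.** The protocol defines effectiveness as conversion to sinus rhythm for at least one minute within 90 minutes of the start of the first infusion (Protocol 9.1 and secondary objective 4). The SAP keeps that endpoint and adds another. SAP 3.3, under effectiveness of vernakalant IV: "Additionally, the proportion who are converted to sinus rhythm regardless of timing will be reported". SAP 5.10: "The rate of successful conversion to sinus rhythm without time restriction will also be expressed" as a proportion, with a 95% confidence interval. The sentence in 5.10 on the 90-minute rate names both analysis populations. The sentence on the unrestricted rate names none and gives no end of observation. SAP 3.4 defines only the 90-minute rate. The Table 15a shell has no row for the unrestricted rate.

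Other cardioversion therapy is handled in these places:

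- SAP 4.2 defines the effectiveness population as everyone in the overall set "EXCEPT those who receive ECV or IV Class I/III AA for cardioversion within 90 minutes of start of the first vernakalant IV administration". It adds that for effectiveness "both analysis population and effectiveness population may be used".
- Table 2, footnote 3, repeats the exclusion with the same 90-minute limit.
- Table 15a, footnote 3, counts patients in the overall set who, within 90 minutes, "have conversion to sinus rhythm for at least one minute but have no ECV or IV Class I/III AA within overall analysis population". Footnote 4 adds oral propafenone and flecainide.

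Therapies to restore sinus rhythm are recorded for much longer than 90 minutes. In stays exceeding 24 hours they are recorded "up to a maximum of 7 days following last infusion of vernakalant IV" (Protocol 7.1).

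**The concern.** An exclusion that ends at 90 minutes suits an outcome that ends at 90 minutes. Once the outcome has no time limit, the exclusion covers only the first part of the period in which rescue can occur. Consider a patient who does not respond, is shocked at three hours and then goes into sinus rhythm. That patient stays in the effectiveness population, stays in the overall set, and meets the literal definition of a patient with successful conversion. In the overall set even rescue before 90 minutes is not excluded for this rate, because footnotes 3 and 4 of Table 15a govern only the 90-minute rows.

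Late rescue is foreseeable from the plan itself. Table 13a has a column for electrical cardioversion at any time after the start of the first infusion, next to the 90-minute column. Table 12a has columns for IV anti-arrhythmics up to 4 hours after the start of the first infusion and outside the 4-hour windows. SAP 4.3 lists IV class I/III use within 4 hours after the start of infusion as a contraindication, so IV drug rescue outside that window also falls outside the 90-minute exclusion.

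At stake is the meaning of one figure in the interim and final reports (SAP 5.11). It would appear as effectiveness of vernakalant but could measure sinus rhythm by any means. Two programmers following the text could produce different numbers.

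**Working it through.** **What the plan states.** No expected value or precision is given for any conversion rate in this study, so there is no stated figure to correct. The plan's worked precision example concerns the health outcomes of interest (SAP 4.1: expected proportion 0.003, N=1,500). Clopper-Pearson limits with x = 0.003 × 1,500 = 4.5 are 0.0009 and 0.0073, with margin 0.0043. These round to the stated 0.001, 0.007 and 0.004. This checks the interval method only; the point does not depend on it.

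**Inputs for the illustration.**

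- Conversion by vernakalant, p = 51.1%: the phase III figure in Protocol section 3, assumed to apply here.
- N = 2,000 treatment episodes (SAP 4.1).
- f, the share of non-converters given another cardioversion after 90 minutes: not in the documents; assumed 10% to 75%.
- s, the share of those restored to sinus rhythm: not in the documents; assumed 50% to 90%.

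**Rate if late rescue is counted as non-success.** 0.511 × 2,000 = 1,022; 1,022/2,000 = 51.1%, exact 95% CI 48.9% to 53.3%, half-width about 2.2 points.

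**Rate if late rescue successes are counted.** Apparent rate = p + (1 − p) × f × s. For example:

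- f = 10%, s = 50%: 0.511 + 0.489 × 0.10 × 0.50 = 53.5%
- f = 75%, s = 90%: 0.511 + 0.489 × 0.75 × 0.90 = 84.1%

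| Late rescue (f) | s = 50% | s = 70% | s = 90% |
|---|---|---|---|
| 10% | 53.5% (+2.4) | 54.5% (+3.4) | 55.5% (+4.4) |
| 25% | 57.2% (+6.1) | 59.7% (+8.6) | 62.1% (+11.0) |
| 50% | 63.3% (+12.2) | 68.2% (+17.1) | 73.1% (+22.0) |
| 75% | 69.4% (+18.3) | 76.8% (+25.7) | 84.1% (+33.0) |

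With an assumed base of 70% the same ranges give 71.5% to 90.2%.

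**Lower bound.** If the recorded conversion is already limited to conversion by vernakalant, rescue successes never enter the numerator and the difference is zero, whatever f and s are.

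The table covers rescue after 90 minutes only. Rescue before 90 minutes in the overall set would be additional.

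**The case against.** A reader might infer that rescue successes will certainly be credited to vernakalant. The documents do not support that. Time to successful conversion is collected under dosing and administration of vernakalant, while other sinus-rhythm therapies are a separate data element (Protocol 7.1.1). Success of electrical cardioversion is its own per-episode item (SAP 5.9, Table 13a). The footnotes to Table 16.3.1 distinguish conversion attributed to vernakalant, with its own date and time, from pharmacological and electrical cardioversion. The case report form is not among the documents, so the conversion field may already carry that attribution. This stands, and it is why the conclusion is that rescue can be counted, not that it will be. It does not remove the gap: SAP 3.4 does not define such an attribution, and 3.3 and 5.10 do not use it for this rate.

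A reader might also take the upper part of the table as an estimate. It is not one: the documents give neither the frequency nor the success of late rescue.

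Nor does the gap compromise the effectiveness result as a whole. The protocol's endpoint is the 90-minute rate, and its rescue rules match its time window. The registry has a single arm and its primary objectives are safety, dosing and risk minimisation. The unrestricted rate therefore carries no hypothesis and estimates no comparative drug effect.

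Finally, a rule based on order of events needs times that some patients lack. Time to conversion may be unavailable retrospectively (Protocol 7.2.1), and vernakalant date/time may be missing for retrospective patients (footnotes to Tables 12a and 13a). Protocol Appendix I projects 435 retrospective patients, and nothing is imputed (SAP 4.4). This stands, and the fix must provide for it.

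**Conclusion.** The gap is real and its consequence is conditional. SAP 3.3 and 5.10 define a conversion rate with no time limit, while every rescue rule in the SAP ends at 90 minutes and the overall analysis set has no rescue exclusion. On the literal text, later electrical or drug cardioversion successes can be counted as conversions by vernakalant.

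The size is unknown. It ranges from zero, if the conversion field is already attributed to vernakalant, to about 33 points at the top of the assumed ranges. If rescue is counted, the smallest case shown at the 51.1% base (2.4 points) is slightly larger than the confidence interval half-width at N = 2,000 (about 2.2 points). The interval would not warn a reader of the difference.

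The affected figure is a descriptive addition in the SAP to a secondary objective. It is worth correcting because the SAP already applies the right logic in Table 15a and only fails to carry it past 90 minutes.

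**What to change.** In SAP 3.3, 3.4 and 5.10:

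1. Name the population used for the unrestricted rate.
2. Count a conversion only if it occurs before the first electrical cardioversion or other anti-arrhythmic drug, IV or oral, given for cardioversion.
3. Classify later conversions as not converted by vernakalant, or report them on a separate line.
4. Show patients with missing conversion or therapy times, mainly retrospective ones, as order unknown.
5. Add the matching row to Table 15a, with this definition as a footnote.

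The alternative is to delete the unrestricted rate from 3.3 and 5.10, since the protocol's endpoint does not need it.

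The cost is a few sentences of SAP text, one table row and slightly more programming. Therapy timings are already planned for Tables 12a and 13a, so no new data item is needed where those times were recorded. The reported rate may be lower, and part of the retrospective group may fall into the unknown category.
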